8.7 CLDQ-NAFLD Scoring

The CLDQ-NAFLD questionnaire ([Protocol Appendix 7](#)) is a disease-specific quality-of-life instrument for nonalcoholic fatty liver disease and NASH. The CLDQ-NAFLD consists of 36 items in 6 domains: abdominal symptoms, activity, emotional function, fatigue, systemic symptoms, and worry. Each item is on a Likert scale with 1 representing the most impairment and 7 representing the least impairment.

Each domain score is an average of its constituent items, and the overall score is an average of the six domains. Any out-of-range value will be considered missing.

In case of missing values, calculation of the domain scores will only be derived when at least 50% of the items are completed, and the total score will require at least three domains.

Items and domains: Ni refers to score obtained for question i.

Abdominal symptoms (AS) = Mean of N1+N5+N17

Activity/Energy (AE) = Mean of N7 + N9 + N14 + N30+ N31

Emotion (EM) = Mean of N10 + N12 + N15 + N16 + N19 + N20 + N24 + N26 + N34

Fatigue = Mean of N2 + N4 + N8 + N11 + N13 + N35

Systemic (SY) = Mean of N3 + N6 + N21 + N23 + N27 + N36

Worry (WO) = Mean of N18 + N22 + N25 + N28 + N29 + N32 + N33

Overall = Mean of six domains

8.8 EQ-5D-3L Scoring

The EQ-5D-3L questionnaire ([Protocol Appendix 6](#)) is a general quality-of-life instrument that consists of 2 components, health state description and evaluation. The health state description component measure mobility, self-care, usual activities, pain/discomfort, and anxiety/depression. Participants will rate their level of impairment in each dimension using a 3-level scale. In the evaluation component, participants evaluate their overall health status using a visual analog scale. Any out-of-range value will be considered missing.

The [REDACTED] programming team will also calculate a United States population-based utility index according to [Shaw et al. 2005](#), using a validated program provided by BMS. The index score will not be generated when responses are missing for one or more of the five dimensions.

8.9 SF-36 (Version 2)

The SF-36 (see [Protocol Appendix 5](#)) is a 36-item instrument. Items are divided into eight concepts plus one health comparison question.

The [REDACTED] programming team will use [REDACTED] software [REDACTED] to score the SF-36.

The raw scale scores are computed by summing item responses within each concept after recoding the individual item if needed.

The eight concepts to be scored are:

Physical Functioning (PF) (items 3a-3j): The ten items are coded as 1-3. There is no recoding needed. The lowest possible raw score is 10, the highest is 30 and the range is 20. High score indicates better PF.

Role-Physical (RP) (items 4a-4d): The items are coded as 1-5. There is no recoding needed. The lowest possible raw score is 4, the highest is 20 and the range is 16. High score indicates better Role- Physical function.

Sponsor: Bristol-Myers Squibb

Protocol no: MB130-068

Role-Emotional (RE) (items 5a-5c): The items are coded as 1-5. There is no recoding needed. The lowest possible raw score is 3, the highest is 15 and the range is 12. High score indicates better Role-Emotional function.

Social Functioning (SF) (items 6, 10): The items are coded as 1-5. Item 6 is recoded as 5-1. Item 10 does not require recoding value. The lowest possible raw score is 2, the highest is 10 and the range is 8. High score indicates better social functioning.

Bodily Pain (BP) (items 7 & 8): This concept requires special coding. Item 7 is coded as 1-6 and is recoded as 6.0, 5.4, 4.2, 3.1, 2.2, 1.0. Item 8 is coded as 1-5 and is recoded as 6-1 if both item 7 and item 8 are answered. If item 7 is not answered, item 8 is recoded as 6.0, 4.75, 3.5, 2.25, 1.0. The lowest possible raw score is 2, the highest is 12 and the range is 10. High score indicates lack of bodily pain.

Mental Health (MH) (items 9b, 9c, 9d, 9f & 9h): The items are coded as 1-5. Items 9b, 9c and 9f do not require recoding. Items 9d and 9h are recoded as 5-1. The lowest possible raw score is 5, the highest is 25 and the range is 20. High score indicates better mental health.

Vitality (VT) (items 9a, 9e, 9g, 9i): The items are coded as 1-5. Items 9a and 9e are recoded as 5-1. Items 9g and 9i do not require recoding. The lowest possible raw score is 4, the highest is 20, the range is 16. High score indicates more vitality.

General Health (GH) (items 1, 11a-11d): The items are coded as 1-5. Items 11a and 11c do not require recoding. Items 11b and 11d are recoded as 5-1. Item 1 is recoded as 5.0, 4.4, 3.4, 2.0, 1.0. The lowest possible raw score is 5, the highest is 25 and the range is 20. High score indicates better general health perceptions.

Reported Health Transition (HT) (item 2). Item 2 is coded as 1-5 and is recoded 5-1.

Any out-of-range value will be considered missing.

Missing or blank values will be estimated using the average recoded score for each concept.

The formula for the transformed scale = [(actual raw score - lowest possible raw score)/Possible raw score range] x 100. The raw scores will be transformed to a 0 – 100 scale.

In addition to the eight concepts above, the scoring software also provides results for two aggregate scores: Physical Component Summary (PCS) and Mental Component Summary (MCS).

8.10 Other Calculations

- ELF assessment combines hyaluronic acid, procollagen 3 amino terminal peptide, and TIMP-1 (tissue inhibitor of metalloproteinases 1). A proprietary algorithm is used to evaluate each of these markers by immunoassay, to create an ELF Score which is provided by an external vendor.
- FIB4 Score = (age [years] × AST level [U/L]) / (platelet count [$\times 10^9/L$] × square root of ALT [U/L]).
- APRI Score = ([AST divided by AST Upper Limit of Normal]/platelet count [$\times 10^9/L$]) × 100
- NAFLD Fibrosis Score = $-1.675 + (0.037 \times \text{age [years]} + (0.094 \times \text{BMI [(kg/m}^2\text{)]}) + (1.13 \times \text{Impaired Fasting Glucose or diabetes [yes = 1, no = 0]}) + (0.99 \times \text{AST/ALT ratio}) - (0.013 \times \text{platelet count [x 10}^9\text{/L}] - (0.66 \times \text{albumin [g/dL]})$). Note, the status of impaired fasting glucose or diabetes (yes or no) will be assessed only once at baseline as recorded by the site in the Specific Disease History eCRF page. This value will be used for all subsequent calculations.

Note for FIB4, APRI, and NAFLD Fibrosis scores that if any one component is missing at a given time point, another non-missing value within an absolute range of 3 days may be used. If there is more than one value that is within 3 days, the closest value after the visit date will be selected. Otherwise, if all components are not available the score will not be calculated at that time point.

Sponsor: Bristol-Myers Squibb

Protocol no: MB130-068

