8.5.1 Efficacy Assessments

Every effort must be made to ensure that the same evaluator(s) complete the assessment for each participant. If the evaluator(s) is unable to complete the evaluation, then a qualified individual with overlapping experience may perform the evaluation. Documentation of who performed the evaluation is to be recorded in source documents. Assessments should be performed at approximately the same time of day throughout the duration of the study. Baseline assessments must be performed prior to dosing with study medication. Procedures not specified in the protocol that are part of standard care may be performed if they do not interfere with study procedures; any data arising from such procedures are not to be reported in the eCRF.

All efficacy assessments will be completed prior to study medication administration. Participant questionnaires will be administered electronically, and information gathered electronically (i.e., electronic patient-reported outcome) will serve as the source document where possible.

The following procedures or tools will be used to assess participant's disease activity during the study (see the Schedule of Activities in [Section 1](#)):

- Liver biopsy (see [Section 8.5.1.1](#)) submitted to the central pathologist at Screening, and at Week 24 or the ET Visit, if applicable
 - Histological assessments of fibrosis stage and NASH activity
 - Assessments of CPA and fat in stained tissue by morphometry
 - Assessments of fibrosis using digital pathology
- Noninvasive measures of fibrosis and/or cirrhosis
 - Noninvasive scores of hepatic fibrosis (see [Section 8.5.1.2](#)) (AST-Platelet Ratio Index [APRI], Fibrosis 4 [FIB4] Index, Enhanced Liver Fibrosis [ELF] Score, NAFLD Fibrosis Score) at Day 1, Week 24, and Week 48 (or the ET Visit, if applicable)
 - Liver stiffness as determined by MRE (see [Section 8.5.1.3](#)) at Screening, Week 24, and Week 48 (or the ET Visit, if applicable)
- Hepatic fat fraction as determined by MRI-based proton density fat fraction (PDFF; see [Section 8.5.1.3](#)) at Screening, Week 24, and Week 48 (or the ET Visit, if applicable)
- Physical metabolic assessments (see [Section 8.5.1.5](#)) at Screening, Day 1, Week 24, and Week 48 (or the ET Visit, if applicable)
 - Body weight
 - Body mass index (BMI)
 - Waist circumference
- Laboratory Metabolic Assessments (see [Section 8.5.1.5](#)) at Screening, Day 1, Week 24, and Week 48 (or the ET Visit, if applicable)
 - Lipids (LDL, HDL, TGs)

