4.5 Exploratory Endpoints

Exploratory endpoints include the following:

- Quantitative measurements of fibrosis and fat on biopsy
 - Assessment of NASH CRN Fibrosis Score at Week 24
 - Proportion of participants with >=2 stage improvement
 - Changes in Fibrosis (as expressed by Shift from baseline)
 - Proportion of participants with >=1 stage improvement, no change, or worsening
 - Assessment of Ishak Fibrosis Score at Week 24
 - Proportion of participants with >=2 stage improvement
 - Changes in Fibrosis (as expressed by Shift from baseline)
 - Proportion of participants with >=1 stage improvement, no change, or worsening
 - Assessment of Fibrosis and NASH using digital pathology at Week 24
 - Absolute, percent change, and change from baseline
 - Assessment of CPA at Week 24
 - Proportion of participants with any improvement
 - Absolute, percent change, and change from baseline
 - Assessment of fat in stained tissue by morphometry and alpha smooth muscle actin (SMA) at Week 24
 - Absolute, percent change, and change from baseline
- Assessment of NAS score at Week 24
 - Changes in NAS (as expressed by shift from baseline, for each individual NAS components (Steatosis, inflammation, Ballooning) as well as Total score)

Sponsor: Bristol-Myers Squibb

[figure not shown]
Protocol no: MB130-068

- Proportion of participants with improvement, no change, or worsening in NAS Total
- Assessment of NASH using digital pathology
 - Absolute, percent change, and change from baseline
- Hepatic fat fraction as measured using MRI-PDFF at Week 24 and Week 48
 - Absolute, percent change, and change from baseline
 - Proportion of subjects in each treatment group with $\geq 30\%$ relative reduction, $\geq 20\%$ relative reduction, $\geq 10\%$ relative reduction, and $\geq 5\%$ absolute reduction
- Noninvasive measures of fibrosis and/or cirrhosis
 - Liver stiffness as determined by Magnetic Resonance Elastography (MRE) at Week 24 and Week 48
 - Absolute, percent change, and change from baseline
 - Proportion of subjects in each treatment group with $\geq 19\%$ or $\geq 15\%$ reduction
- Noninvasive scores of hepatic fibrosis (AST-Platelet Ratio Index (APRI), Fibrosis 4 (FIB-4), Enhanced Liver Fibrosis (ELF), and NAFLD Fibrosis Score) from Day 1 to Week 24 and Week 48
 - Absolute, percent change, and change from baseline
 - Proportion of participants in each ELF category by time point
- Metabolic assessments at Week 24 and Week 48

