8.0 Conventions and General Definitions

8.1 General Definitions

Term	Definition
Study Day	Study day is calculated as: assessment date – date of first dose + 1
Baseline	Unless otherwise stated, Baseline is defined as the last measurement prior to dosing on Day 1 (Week 0). If the measurement on Day 1 is missing or not available, then a prior measurement during the screening period may be used as baseline.
Change from Baseline	Change = Value at post-baseline visit – value at baseline
Change in the maximum post-baseline value	Change = Highest observed value post-baseline – value at baseline
Percent Change from Baseline	Percent change from baseline is defined as ([value at post-baseline visit – value at baseline]/value at baseline) x 100. If the baseline value is 0 and the post-baseline value is also 0, then the percent change from baseline is set to 0.
Study Treatment	For the purposes of the calculations included in this SAP, study treatment will include only doses of BMS-986036 (dose levels of 10 mg QW, 20 mg QW or 40 mg QW) or placebo QW.
Duration of Study Treatment	Duration of study treatment in weeks will be defined as: (date of last dose of study treatment – date of first dose of study treatment+7)/7.
Treatment Completion (%)	Treatment completion (%) will be calculated as the total number of treatment doses received divided by the total number of expected doses (48), multiplied by 100.
End of Study (EOS) Date	The EOS date is the date recorded on the eCRF that a participant either discontinued or completed the study. If the participant is lost to follow-up, the EOS date will be the date of the last visit assessment obtained.
First Dose Date – Study	The date a participant received their first dose as recorded in the eCRF as date study treatment was administered.
Last Dose Date – Study	The date of last recorded dose on the eCRF for a subject.
Unscheduled assessments	Unscheduled measurements will be included in the listings. With the exception of unscheduled measurements used for baseline and unscheduled measurements will be excluded from the descriptive statistics and statistical analysis.

Sponsor: Bristol-Myers Squibb

Protocol no: MB130-068

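### The 3-day substitution rule for FIB-4, APRI and the NAFLD Fibrosis Score has no Day 1 exception, so it can put a post-dose value into the baseline score

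*SAP*

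**What the plan says.** SAP 8.10 gives one rule for all three scores at any time point. If a component is missing, "another non-missing value within an absolute range of 3 days may be used". Where several values qualify, "If there is more than one value that is within 3 days, the closest value after the visit date will be selected". Failing that, "Otherwise, if all components are not available the score will not be calculated at that time point". Nothing is said about Day 1.

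SAP 4.5 lists the noninvasive scores "and NAFLD Fibrosis Score) from Day 1 to Week 24 and Week 48", and Protocol 8.5.1 schedules them at Day 1, Week 24 and Week 48. Day 1 is therefore their starting point.

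SAP 8.1 defines baseline, unless otherwise stated, as the last measurement before the Day 1 dose. It adds: "If the measurement on Day 1 is missing or not available, then a prior measurement during the screening period may be used as baseline". Protocol 8.5.1 says: "Baseline assessments must be performed prior to dosing with study medication".

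For several records in one visit window, SAP 8.3 takes the one nearest the planned visit day. It has no preference for later values.

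**The concern.** A window that reaches 3 days either side of a visit is harmless at Week 24 or Week 48, when the participant is on treatment on both sides. At Day 1 it straddles the first dose. A value from Days 2 to 4 is an on-treatment value, and Protocol 6.1.2 puts the median time to maximum concentration after a single dose at 24 to 33 hours. Used as a baseline component, it would place part of any early treatment effect in the reference value from which change is measured.

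Two SAP sections can also give different baselines for the same participant, or a baseline under one and none under the other. Neither section says which governs. SAP 8.1 yields where something else is stated, and SAP 8.10 is the specific rule for these scores, so two programmers could reasonably differ.

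**Working it through.** The documents state no figure for this rule, so there is nothing to reproduce. The check applies both rules to the same dates and then looks at when such dates can arise.

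**1. The two rules side by side.** Suppose one component is missing on Day 1. The left column gives the days, relative to Day 1, on which that component was measured. The Screening sample at day −28 is an example date.

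| Values available | SAP 8.10, read literally | SAP 8.1 |
|---|---|---|
| −28 | none; score not calculated | −28 |
| −28, −2 | −2 | −2 |
| −28, +2 | +2 (post-dose) | −28 |
| −28, +1, +3 | +1 (post-dose) | −28 |
| −28, −1, +3 | +3 (post-dose) | −1 |
| −28, −3, −1 | undefined | −1 |

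A single pre-dose value in the window is handled correctly. A single post-dose value enters through the two-sided window; the tie-break plays no part. The tie-break does harm in the fifth row, where it passes over a value that is both closer and pre-dose. In the last row two values qualify but none follows the visit, so the rule gives no answer.

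**2. Where a Day 2 to 4 value could come from.** The first scheduled hematology and chemistry after Day 1 are at Week 4 ± 5 days. Week 4 is Day 7 × 4 + 1 = 29, so the earliest is Day 29 − 5 = 24, which is 23 days after Day 1. No scheduled sample can fall on Days 2 to 4. Protocol 8.5.4 does allow repeat laboratory tests at the investigator's judgment, so an unscheduled one could.

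**3. Whether Screening data exist.** Protocol Table 1 lists hematology, blood chemistry, height and weight at Screening. With age and with the diabetes status that SAP 8.10 records once, that covers all the inputs of the three scores. A complete Screening score can be computed.

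**4. What one substituted value could do.** The documents give no effect for Days 2 to 4. As an illustration only, let a component have changed by between 0 and −26.7%. The lower end is the model-predicted ALT change at 40 mg in Protocol Table 4, which is at trough under weekly dosing and is not a first-week figure; the same range is assumed for AST. With f = 1 − 0.267 = 0.733:

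- ALT alone: FIB-4 varies as 1/√ALT, and 1/√0.733 = 1.168, a shift of 0 to +16.8%.
- AST alone: FIB-4 and APRI vary in proportion to AST, a shift of 0 to −26.7%.
- Both: FIB-4 varies as f/√f = √0.733 = 0.856, a shift of 0 to −14.4%.
- ALT alone, NAFLD Fibrosis Score, with a true AST/ALT ratio of 1: 0.99 × (1/0.733 − 1) = 0.36, a shift of 0 to +0.36.

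These are shifts in one participant's baseline. They are not effects on a treatment comparison.

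**The case against.** The best defence is that the conditions are unusual and other text points the right way. Dosing on visit days is held until the laboratory samples are drawn. A post-dose substitute needs both a missing Day 1 component and an unscheduled test on Days 2 to 4. For it to displace a pre-dose value, there must also be a value on Days −3 to −1. The wording in SAP 8.10 is permissive. SAP 8.1 keeps unscheduled values out of the analysis except when used for baseline, and it defines baseline as pre-dose. All of this stands as an argument that the problem is rare. It does not remove the conflict: the sentence on unscheduled values is garbled, and nothing makes SAP 8.1 prevail over the specific rule.

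A reader might infer that participants with no value within 3 days are lost from every change-from-baseline analysis despite having a Screening sample. The documents do not support that. SAP 8.10 leaves the score uncalculated only at that time point and does not redefine baseline, and SAP 8.1 allows a Screening measurement to serve. The loss would follow only if SAP 8.10 overrides SAP 8.1, which is not stated. What remains is an open question.

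At later visits, preferring the after-visit value is prespecified and the same in every arm. No between-arm bias follows from it. It departs from SAP 8.3 without a stated reason and leaves the two-earlier-values case undefined.

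**Conclusion.** The point holds as a gap in a written rule. Read literally, SAP 8.10 can produce a baseline score containing a post-dose value, contrary to SAP 8.1 and Protocol 8.5.1. It is also silent on the Screening fallback and undefined when both candidate values precede the visit.

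The consequence is minor. It concerns exploratory scores only; the primary and secondary biopsy endpoints are untouched. Its frequency cannot be obtained from the documents. A reader might assume a tube-failure rate and turn it into a head count: at 1% to 3% for each of two tubes, 1 − (1 − p)² is 2.0% to 5.9%, or about 4 to 12 of 197. That would count participants with any missing Day 1 tube, not participants given a wrong baseline. Most of them would have no test on Days 2 to 4 if such tests are as uncommon as the schedule suggests, and the Screening fallback may cover them. Nor does the rule generally build the baseline from post-dose data; it can do so only in the circumstances described.

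**What to change.** Add to SAP 8.10:

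*For the Day 1 (baseline) score, only pre-dose component values may be substituted, the latest being taken if there is more than one. If none lies within 3 days, the most recent complete Screening score serves as baseline under Section 8.1. At post-baseline visits the value closest to the visit date in either direction is used, consistent with Section 8.3; if two are equidistant, the earlier is used.*

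At Day 1 this gives a pre-dose baseline for every date pattern in the table, provided the Screening score is complete. Falling back to a whole Screening score also avoids combining, say, a Day 1 AST with a much older platelet count.

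The cost is a few sentences and a small programming change, with no new data. The one downside is that a Screening score used as baseline may be up to 12 weeks old, since Protocol 8.1 allows Screening to be extended to that length.

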Appendix 1 Glossary of Abbreviations

Glossary of Abbreviations:

ADA	anti-drug antibody
AE	adverse event
AESI	adverse event of special interest
ALT	alanine aminotransferase
ANCOVA	analysis of covariance
APRI	AST-to-platelet ratio index
AST	aspartate aminotransferase
AUC	area under the concentration-time curve
ATC	anatomic therapeutic classification
BMD	bone mineral density
BMI	body mass index
BMS	Bristol-Myers Squibb
COVID-19	corona virus disease - 19
CI	confidence interval
CMH	Cochran Mantel-Haenszel
CPA	collagen proportionate area
CLDQ	chronic liver disease questionnaire
Cmax	maximum observed concentration
CRN	clinical research network
CSR	clinical study report
CV	coefficient of variation
DMC	data monitoring committee
DXA	dual-energy X-ray absorptiometry
eCRF	electronic case report form
ECG	electrocardiogram
eGFR	estimated glomerular filtration rate
ELF	enhanced liver fibrosis
EOS	end of study
EQ-5D-3L	3-Level EuroQol 5 Dimension (quality-of-life questionnaire)

Sponsor: Bristol-Myers Squibb

Protocol no: MB130-068

ET	early termination
FGF21	fibroblast growth factor 21
FIB4	fibrosis 4
HDL	high-density lipoprotein
HT	health transition
ICH	international conference on harmonization
IRS	independent reporting statistician
IRT	interactive response technology
LDL	low-density lipoprotein
LLOQ	lower level of quantification
MCS	mental component summary
MedDRA	medical dictionary for regulatory activities
miITT	modified intent-to-treat
MRE	magnetic resonance elastography
MRI-PDFF	magnetic resonance imaging-proton density fat fraction
NAFLD	nonalcoholic fatty liver disease
NAS	NAFLD activity score
NASH	nonalcoholic steatohepatitis
NEC	not elsewhere classified
PCS	Physical Component Summary
PD	pharmacodynamic
PEG	polyethylene glycol
PK	Pharmacokinetic
PRO-C3	N-terminal type 3 collagen propeptide
PT	preferred term
PTFU	post-treatment follow-up
QC	quality control
QTcF	QT interval corrected using Fridericia's formula
QW	once weekly
SAE	serious adverse event
SAP	statistical analysis plan
SC	subcutaneous

Sponsor: Bristol-Myers Squibb

Protocol no: MB130-068

SD	standard deviation
SOC	system organ class
SF-36	36-question Short Form quality-of-life questionnaire (Version 2)
SMA	smooth muscle actin
T2DM	type 2 diabetes mellitus
TEAE	treatment-emergent adverse event
TFLs	tables, figures, and listings
TG	triglycerides
TIMP-1	tissue inhibitor of metalloproteinases 1
Tmax	time take to reach Cmax
ULN	upper limit of normal
WHO	world health organization
WHODD	world health organization drug dictionary

Sponsor: Bristol-Myers Squibb

Protocol no: MB130-068

